9.1.1 Tumour Biopsy Assessment

Pre-treatment biopsies will be performed up to 28 days prior to the start of treatment and on-treatment biopsies will be obtained between days 8 and 14 of cycle 1 of treatment.

Immunofluorescence (IF) assays will be employed to examine co-localization of free cholesterol (FILIPIN stain) with late endosomes/ lysosomes (LAMP1 stain). IHC will also be employed to

assess the presence of NPC1, SCP2 and STARD3 as markers of cholesterol trafficking. Bodipy lipid staining will be performed to detect levels of free and esterified cholesterol.

RNA will be extracted for a custom PCR array of genes involved in lipoprotein signaling, cholesterol transport, synthesis and metabolism, and autophagy.

IHC LC3B, p62, caspase 3 cleavage products, gamma-H2AX and Ki67 as markers of autophagy (LC3B/p62), apoptosis (caspase 3 cleavage products and gamma-H2AX) and proliferation (Ki67). IHC for CD31 and HIF-1α will be done to investigate the role of angiogenesis.

Next generation sequencing for mTOR, AKT-PI3K pathway genes will be performed to investigate their role in resistance and authophagy.

If there are is any tissue remaining after the above mentioned investigations are completed, it will be banked for future use to validate and investigate as yet unknown biomarker targets or mechanisms of action.

9.1.1.1 Opportunistic tissue collection

Patients undergoing a biopsy or drainage of pleural fluid or ascites for diagnostic or therapeutic purposes may have a sample stored for future research on as yet unknown biomarkers or mechanisms of action. This collection is optional.

9.1.1.2 Collection of Specimens

Archival slides and tumor biopsies will be obtained. Refer to the study-specific Laboratory Manual for detailed collection and processing procedures.

9.1.1.3 Handling of Specimens

Refer to the study-specific Laboratory Manual for detailed collection and processing procedures.

9.1.1.5 Site Performing Correlative Study

Princess Margaret Cancer Centre will be the site performing correlative studies for archival tissue.

9.1.2 Peripheral Blood Assessment

Peripheral blood cells, plasma, and serum will be isolated from phlebotomy specimens. These samples will be used fresh or stored for future analysis. Blood will be analyzed colorimetric/flow cytometry to characterize/quantify free and esterified cholesterol accumulation.

If there are is any tissue remaining after the above mentioned investigations are completed, it will be banked for future use to validate and investigate as yet unknown biomarker targets or mechanisms of action.

9.1.2.1 Shipping of Specimens

Heparinized blood must be kept at room temperature after collection. Blood for sera should be kept upright at room temperature and clot for 30-60 minutes. Centrifuge blood at 1500g for 15 minutes. Divide serum evenly into two aliquots. Freeze samples at -70°C and store until shipping.

Refer to the study-specific Laboratory Manual for detailed collection and processing procedures.

9.1.2.2 Handling of Specimens

Blood specimens will be sent to the Correlative Studies Program (PM Cancer Centre): Correlative Studies Program

Princess Margaret Cancer Centre

[name] [name] [contact] [name]

[contact]

Email: [contact]

Specimens must be shipped Monday through **Wednesday**. For any samples collected on a Friday, the samples should be **processed on site**, and shipped out the following Monday. If sites are unable to process the PBMC locally, they MUST ship the sample Mon-Wed to the Correlative Studies Program. PBMC samples should not be collected on a Thursday or Friday unless the site is able to complete the processing.

9.1.2.3 Site Performing Correlative Study

Princess Margaret Cancer Centre will be the site performing correlative studies for peripheral blood.

9.1.2.4 Collection of Specimens

Bloods include 3 x 10 ml tubes for heparinized blood, and one 5 ml tubes for sera (SST tube). Blood will be obtained at the following study visits: Pre-study, Day 1 and 8 on study.

10. STUDY CALENDAR

Baseline (pre-study) evaluations are to be conducted within 28 days prior to start of protocol therapy, unless specified differently in the study calendar. Scans and x-rays must be done within 28 days prior to the start of therapy. In the event that the patient's condition is deteriorating, laboratory evaluations should be repeated within 48 hours prior to initiation of the next cycle of therapy. The following schedule of assessments applies to all subjects. More frequent assessments should be obtained if clinically indicated. For subsequent cycles 2+, day 1 assessments can be completed up to 2 days prior to day 1. A cycle is 28 days long for the purposes of this protocol.

	Pre-	Pre		C;	ycle 1			Cycl	e 2+		Off Treatment
	Study (within 28 days)	study (within 10 days)	D 1	D 8 (+/- 2 days)	D 15 (+/- 2 days)	D 22 (+/- 2 days)	D 1 (+/- 2 days)	D 8 (+/- 2 days)	D 15 (+/- 2 days)	D 22 (+/- 2 days)	(30-37days after last dose) ^c + Follow-Up ^f
Itraconazole	• /	• /	A							A	
Hydroxychloroquine			В							В	
Informed consent	X										
Demographics	X										
Medical history	X										
Concurrent meds	X		X							X	
Physical exam	X		X	X	X	X	X				X
Vital signs (Blood pressure, pulse, respiratory rate, temperature)	X		X	X	X	X	X				X
Height	X										
Weight	X		X				X				X
Performance status	X		X	X	X	X	X				X
CBC w/differential	X	X	X	X	X	X	X				X
Serum chemistry ^a	X	X	X	X	X	X	X				X
Ca 125	X		X				X				
EKG	X		X				X				
MUGA or echocardiogram	X										
Eye Assessment ^j	X				to be	perform	ed every	2 cycles			
Adverse event evaluation]	X						X	X
Tumor measurements	X					are done Docume					Xg

		-	rovided for patients removed from study for progressive isease.							
Radiologic evaluation	X	rega	rdless of rided for	any dela	y in treat	ment. Do	rformed ocumentary	tion mus	t be	Xg
B-HCG	X^{b}									
Tumour biopsy	X^d		X^d							
PBMC & Plasma ^h	Xi		X							
Serum ^h	Xi	X	X							
Opportunistic tissue/fluid collection ^e		XX								

- A: Itraconazole: Dose as assigned; twice daily for 28 days
- B: Hydroxychloroquine: Dose as assigned; twice daily for 28 days
- a: Albumin, alkaline phosphatase, total bilirubin, bicarbonate, BUN, calcium, chloride, creatinine, glucose, LDH, magnesium, phosphorus, potassium, total protein, SGOT [AST], SGPT [ALT], sodium LDL, HDL, total cholesterol, Apolipoprotein B and triglycerides.
- b: Serum pregnancy test (women of childbearing potential).
- c: Off-study evaluation and follow up as described in section 5.5
- d: Pre-treatment biopsy to be done up to 28 days prior to start of therapy. On-treatment biopsy to be done on day 8-14.
- e: Patients undergoing a biopsy or fluid collection for diagnostic or therapeutic reasons may have a sample of their tissue or fluid collected for the purposes of this study.
- f: Patients will be followed every 4 weeks from the End of Treatment visit for 12 weeks or until resolution of adverse events for patients who will come off study due to toxicity.
- g: Only patients who come off study treatment for reasons other than progressive disease (radiological or clinical) need to have scans and RECIST measurements performed. This will occur every 12 weeks from the previous scan until documented progression (radiological or clinical).
- h: Three 10 mL tubes of heparinized blood will be collected for PBMC and plasma isolation, and one 5 mL SST tube for sera.
- i: Samples must be drawn prior to MUGA.
- j. The following eye tests will be performed: Ocular Symptom Assessment, Visual Acuity, Slit Lamp Examination, Intraocular Pressure, Dilated Fundoscopic Examination, Schirmer test and any other diagnostic test.

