5. TREATMENT PLAN

5.1 Agent Administration

Treatment will be administered on an outpatient basis. Reported adverse events and potential risks are described in Section 7. Appropriate dose modifications are described in section 6. No investigational or commercial agents or therapies other than those described below may be administered with the intent to treat the patient's malignancy.

The patient will be requested to maintain a medication diary of each dose of medication. The medication diary will be returned to clinic staff at the end of each course.

Regimen Description					
Agent	Premedications / Precautions	Dose	Route	Schedule	Cycle Length
itraconazole	Take with food	300 mg	PO	twice daily	
hydroxychloroquine	Take with food or milk Antacids should not be taken within 4 hours before or 4 hours after dosing with hydroxychloroq uine	** tablet	PO	** once or twice daily	28 days (4 weeks)
**Doses as appropria	te for assigned dose	e level.	1	1	

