5.3 Rolling Six Design

The rolling six design allows for accrual of 2 to 6 patients concurrently on the same dose level.

The dose of hydroxychloroquine will be escalated in fixed increments according to the dose escalation scheme outlined below.

Dose level	Dose of itraconazole (total daily dose)	Dose of HYDROXYCHLOROQUINE (total daily dose)	Minimum number of patients	Maximum number of patients
	300 mg BID	200 mg OD (200 mg total)		6
-1	(600 mg total)	200 mg 02 (200 mg total)		C
1	300 mg BID	200 mg BID (400 mg total)	2	6
(starting)	(600 mg total)		2	
2	300 mg BID	400 mg BID (800 mg total)	2	6
2	(600 mg total)		2	
3	300 mg BID	600 mg BID (1200 mg total)	2	6
3	(600 mg total)		2	

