5.3.1 Specific Dose Escalation and De-Escalation Rules for this Trial

- Starting dose level is 1.
- The dose level -1 block will be used if and only if dose level 1 is too toxic (i.e. if dose level 1 is above the MTD).

Determination of which dose level to enroll a patient into will be made according to the table below (adapted from [47]). The decision is based on the number of patients currently enrolled on a specific dose level, how many of them experienced DLTs, and how many patients are still pending data on DLTs experienced.

		DLT Data		Enrolling Do	ose Level*
# Currently Enrolled	# Patients with DLTs	# of Patients without DLTs	# of Patients w/Data Pending	When n is lower than Trial Maximum	When n is at Trial Maximum
2	0, 1	Any	Any	n	
2	2	0	0	n - 1	
3	0	0, 1, 2	3, 2, 1	n	
3	0	3	0	n + 1	
3	1	0. 1	2, 1	n	
3	1	2	0	n	
3	≥ 2	Any	Any	n - 1	
4	0	0, 1, 2	4, 3, 2	n	n
4	0	3	1	n	n
4	0	4	0	n + 1	n
4	1	0, 1	3, 2	n	n
4	1	2	1	n	n
4	1	3	0	n	n
4	≥ 2	Any	Any	n - 1	n - 1
5	0	0, 1, 2	5, 4, 3	n	n
5	0	3, 4	2, 1	n	n
5	0	5	0	n + 1	n
5	1	0, 1	4, 3	n	n
5	1	2	2	n	n
5	1	3, 4	1, 0	n	n
5	≥ 2	Any	Any	n - 1	n - 1
6	0	0, 1, 2	6, 5, 4	Accrual hold	Accrual hold
6	0	3, 4	3, 2	Accrual hold	Accrual hold
6	0	5, 6	1, 0	n + 1	RP2D
6	1	0, 1	5, 4	Accrual hold	Accrual hold
6	1	2	3	Accrual hold	Accrual hold
6	1	3,4	2, 1	Accrual hold	Accrual hold
6	1	5	0	n + 1	RP2D
6	≥ 2	Any	Any	n - 1	n - 1

Abbreviations: DLT - dose limiting toxicity; RP2D - recommended phase 2 dose

 $[\]ast$ n is the current dose level of patients enrolled; n + 1 and n - 1 represent dose level escalation and deescalation, respectively.

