6. DOSING DELAYS/DOSE MODIFICATIONS

Doses will be reduced for haematological and other adverse events. Dose adjustments are to be made according to the greatest degree of toxicity. Adverse events will be graded using the NCI Common Terminology Criteria for Adverse Events Version 4.0 (CTCAE).

When a dose is held due to adverse events, the cycle shall continue even if no study medication is received.

The guidelines which follow outline dose adjustments for several of these toxic effects. If a patient experiences several adverse events and there are conflicting recommendations, please use the recommended dose adjustment that reduces the dose to the lowest level.

The major adverse effects of itraconazole and hydroxychloroquine are listed in section 7.

Dose reduction for itrozanole as specified in Table below:

Dose Level	itraconazole
1	300 mg PO BID
-1	200 mg PO BID
-2	100mg PO BID

For dose adjustment of hydroxychloroquine, please refer to dosing guidelines from the phase I component of trial in section 5.2.

Note that patients cannot dose reduce below 200mg OD for hydroxychloroquine and 100 mg BID for itraconazole. Any patients who experience adverse events requiring hydroxychloroquine dose reduction below 200 OD mg or itraconazole below 100 mg BID will stop study related therapy.

Nausea	Management/Next Dose for itraconazole	Management/Next Dose for hydroxychloroquine	
≤ Grade 1	No change in dose	No change in dose	
Grade 2	Hold* until \leq Grade 1. Resume at	Hold* until \leq Grade 1. Resume at	
Grade 2	same dose level.	same dose level.	
Grade 3	Hold* until < Grade 2. Resume at	Hold* until < Grade 2. Resume at	
Grade 3	one dose level lower, if indicated.**	one dose level lower, if indicated.**	
		Off protocol therapy	
*Patients requiring a delay of >2 weeks should go off protocol therapy.			

^{**}Patients requiring > two dose reductions should go off protocol therapy.

Recommended management: Antiemetics and intravenous hydration if required.

Vomiting	Management/Next Dose for	Management/Next Dose for	
vointing	itraconazole	hydroxychloroquine	
≤ Grade 1	No change in dose	No change in dose	
Grade 2	Hold* until \leq Grade 1. Resume at	Hold* until \leq Grade 1. Resume at	
Grade 2	same dose level.	same dose level.	
Grade 3	Hold* until < Grade 2. Resume at	Hold* until < Grade 2. Resume at	
Grade 3	one dose level lower, if indicated.**	one dose level lower, if indicated.**	
Grade 4	Off protocol therapy	Off protocol therapy	
*D.:			

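### Study calendar footnote B fixes hydroxychloroquine at twice daily, contradicting the once-daily 200 mg dose at level -1 and at the lowest reduction step

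*Protocol*

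**What the plan says.** Protocol section 10 (Study Calendar) lists hydroxychloroquine for cycle 1 and for later cycles under footnote B: "B: Hydroxychloroquine: Dose as assigned; twice daily for 28 days". The introduction to the calendar says: "The following schedule of assessments applies to all subjects".

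Other sections provide for a once-daily schedule:

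- Section 5.1 gives the hydroxychloroquine schedule as "once or twice daily", depending on the assigned level.
- The section 5.3 table sets level -1 at "200 mg OD (200 mg total" per day). The synopsis table also shows level -1 as 200 mg once daily.
- Section 5.3.1 restricts the use of that level: "The dose level -1 block will be used if and only if dose level 1 is too toxic".
- Section 6 sets the floor for reductions: "Note that patients cannot dose reduce below 200mg OD for hydroxychloroquine and 100 mg BID for itraconazole".

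For the hydroxychloroquine reduction steps, section 6 says: "For dose adjustment of hydroxychloroquine, please refer to dosing guidelines from the phase I component of trial in section 5.2". Section 5.2 holds the DLT definitions and lists no dose levels. For dose modifications it refers on to section 7, which covers adverse events and their reporting. The hydroxychloroquine dose levels are in section 5.3.

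**The concern.** Footnote B leaves the amount open but fixes the frequency. A patient whose assigned dose is 200 mg once daily therefore has two incompatible frequencies in the same protocol. If the footnote's frequency is applied to the 200 mg intake, the daily dose doubles.

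Two groups are exposed. The first is the level -1 cohort, which opens only after level 1 has proved too toxic. If those patients took the level 1 daily dose, their DLTs would be recorded against half of what they received. That bears on the primary endpoint, the MTD or maximum administered dose that sets the RP2D (section 13.1.3). Two DLTs at level -1 call for a step down in the section 5.3.1 table, and no lower level is listed. The second group is individual patients reduced to 200 mg once daily for toxicity. For a patient coming down from 200 mg twice daily, the ordered reduction would not take effect.

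**Working it through.** **Inputs.** Dose per intake, frequency and stated daily total come from the section 5.3 table. The calendar frequency comes from section 10, footnote B. Tablet strength (200 mg, the only one described) comes from section 8.1.2.

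**Step 1: reproduce the protocol's own totals.** Daily dose = mg per intake × intakes per day.

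| Level | Section 5.3 dose | Computed daily total | Stated total | With the calendar's two intakes | Ratio |
|---|---|---|---|---|---|
| -1 | 200 mg × 1 | 200 mg | 200 mg | 200 × 2 = 400 mg | 2.0 |
| 1 | 200 mg × 2 | 400 mg | 400 mg | 400 mg | 1.0 |
| 2 | 400 mg × 2 | 800 mg | 800 mg | 800 mg | 1.0 |
| 3 | 600 mg × 2 | 1200 mg | 1200 mg | 1200 mg | 1.0 |

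All four stated totals reproduce. Only level -1 changes under the calendar's frequency, and it becomes equal to level 1.

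**Step 2: can both instructions be met at once?** Dividing 200 mg/day into two intakes gives 100 mg each, and 100 / 200 = 0.5 tablet per intake. With whole 200 mg tablets, two intakes a day give at least 400 mg. The phrase about the assigned dose therefore does not reconcile the footnote with level -1.

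**Step 3: who is affected.**

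- Phase I: up to 6 patients at level -1 (maximum in the section 5.3 table).
- Phase II: all patients treated at the RP2D if level -1 becomes that dose. The synopsis gives 9 to 34 patients for phase II.
- Reductions: if steps follow the section 5.3 levels (an assumption, since the section 6 pointer does not lead there), 200 mg once daily is one step below level 1 and two below level 2. From level 3 it would be three steps, and sections 5.5 and 6 take a patient off therapy after more than two reductions.

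**Step 4: the path for a reduced patient.** Section 6 names the floor but sends the reader to 5.2 for the steps, and 5.2 points on to section 7. Neither lists hydroxychloroquine dose levels, so following the references does not reach the 5.3 table that would show the frequency.

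**The case against.** The strongest reply is that nobody would be misled. Footnote B begins by deferring to the assigned dose, and at level -1 that dose is itself defined as once daily. The result is a self-contradictory line that invites a query, not a clear order for 400 mg. The calendar calls itself a schedule of assessments, while administration is governed by section 5.1. The central office assigns the dose at registration and confirms it to the site in writing (section 4.2). Diaries are returned each course (section 5.1), and sites reconcile drug accountability (section 8.1). Every planned escalation level is twice daily, so the footnote is correct for levels 1 to 3 at full dose.

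Much of this stands. A reader might infer that sites will give double the dose. The document does not support that: doubling is a risk of literal reading, and the controls above would have to fail first. A reader might also infer that the doubled dose is always one already declared too toxic. That holds for the level -1 cohort only; an individual may be reduced to 200 mg once daily in a trial where level 1 was tolerated.

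The reply does not remove the contradiction. The confirmation in section 4.2 is tied to registration, and no equivalent is described for a reduction during treatment. Diary return and reconciliation come after doses have been taken. Section 6 does name the once-daily floor, but its pointer for the steps is wrong.

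The sample diary in Appendix E may also print a 12-hour interval for hydroxychloroquine. Its text is scrambled in the copy reviewed, so it is something to check and not part of the evidence.

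**Conclusion.** The point holds as an internal contradiction: footnote B is wrong as written for any patient on 200 mg once daily, or else sections 5.1, 5.3 and 6 and the synopsis are. If the footnote were followed literally with whole 200 mg tablets, the daily dose would be 400 mg instead of 200 mg (2.0 times), the level 1 total. For the level -1 cohort this could attribute DLTs to the wrong dose. For a patient reduced from 200 mg twice daily it could cancel the reduction.

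The scope is narrow and conditional. It is confined to level -1, which opens only if level 1 fails, and to patients reduced to the floor. The number of reduced patients cannot be derived from the protocol. The incorrect section 6 reference is a separate error. It does not cause the frequency conflict, but it removes the most direct way of resolving it during treatment.

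**What to change.** The sponsor should reconcile footnote B with sections 5.1, 5.3 and 6 and the synopsis, so that all state the same frequency for each dose level. The dosing interval in the Appendix E sample diary should be checked against the result. The section 6 reference to 5.2 should be corrected so that it leads to the hydroxychloroquine dose levels. Which dose and schedule are right is for the sponsor to decide.

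The cost is wording in a footnote and a cross-reference, and possibly in the diary template. It needs no additional patients, visits or procedures.

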11. MEASUREMENT OF EFFECT

11.1 Antitumor Effect – Solid Tumors

Patients with measurable disease will be assessed by standard criteria. For the purposes of this study, patients should be re-evaluated for response every 8 weeks. In addition to a baseline scan, confirmatory scans should also be obtained at least 4 weeks following initial documentation of objective response.

In the expansion cohort, tumours will be re-evaluated every 8 weeks during treatment, and at least 4 weeks after the first observation of a complete or partial response. After discontinuation of protocol treatment, patients who have discontinued treatment for reasons other than disease progression will still be re-evaluated every 12 weeks.

Response and progression will be evaluated in this study using the new international criteria proposed by the revised Response Evaluation Criteria in Solid Tumors (RECIST) guideline (version 1.1) [Eur J Ca 45:228-247, 2009]. The published RECIST document is available at http://www.eortc.be/RECIST. Changes in the largest diameter (unidimensional measurement) of the tumor lesions and the shortest diameter in the case of malignant lymph nodes are used in the RECIST criteria.

11.1.1 Definitions

Evaluable for toxicity. All patients will be evaluable for toxicity from the time of their first treatment with itraconazole and hydroxychloroquine.

Evaluable for objective response. Only those patients who have measurable disease present at baseline, have received at least one cycle of therapy, and have had their disease re-evaluated will be considered evaluable for response. These patients will have their response classified according to the definitions stated below. (Note: Patients who exhibit objective disease progression prior to the end of cycle 1 will also be considered evaluable.)

Evaluable Non-Target Disease Response. Patients who have lesions present at baseline that are evaluable but do not meet the definitions of measurable disease, have received at least one cycle of therapy, and have had their disease re-evaluated will be considered evaluable for non-target disease. The response assessment is based on the presence, absence, or unequivocal progression of the lesions.

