13.2 Sample Size/Accrual Rate

The sample size will be a maximum of 52 patients. This will encompass between 6 and 18 on phase I and 34 on for the phase II component.

Phase II sample size:

Stage 1 of accrual: 9 response evaluable patients will be entered in the first stage. Using response hypotheses of H_0 <15 % and H_a >35%, we would reject the drug at the end of the first stage of accrual if no objective responses were seen. Otherwise, an additional 25 patients will be accrued. Patients treated at RP2D in the phase 1 part of the study will be considered for the statistical analysis of the phase 2 stage 1. A total (between phase 1 and phase 2 stage 1) of 9 response evaluable patients treated at RP2D are required.

Stage 2 of accrual: An additional 25 patients will be accrued. We would accept the drug as active if 8 or more objective responses are observed from 25 patients accrued.

Significance level and power: The procedure described above test the null hypothesis that the response rate is 15% versus alternating hypotheses that the response rate is 35%. The significance level (*i.e.*, the probability of rejecting H0 when it is true) is α =0.05 and the power (*i.e.*, the probability of deciding the regimen is active) is 0.81 when true response rate is 20%. The expected sample size with this design is 19 when the null hypothesis is true and 25 when the alternative hypothesis is true.

Accrual and Duration of Study

The estimated accrual for this study is 2-4 patients a month. Thus, patient accrual is expected to be completed within 12-18 months. Additional time is required to allow the response data to mature.

All of the patients registered in the study will be accounted for. The number of patients who were not evaluable, who died or withdrew before treatment began will be specified. The distribution of follow-up time will be described and the number of patients lost to follow-up will be given.

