13.5.2 Evaluation of Response

All patients included in the study must be assessed for response to treatment, even if there are major protocol treatment deviations or if they are ineligible. Each patient will be assigned one of the following categories: 1) complete response, 2) partial response, 3) stable disease, 4) progressive disease, 5) early death from malignant disease, 6) early death from toxicity, 7) early death because of other cause, or 9) unknown (not assessable, insufficient data). [Note: By arbitrary convention, category 9 usually designates the "unknown" status of any type of data in a clinical database.]

All of the patients who met the eligibility criteria (with the possible exception of those who received no study medication) should be included in the main analysis of the response rate. Patients in response categories 4-9 should be considered to have a treatment failure (disease progression). Thus, an incorrect treatment schedule or drug administration does not result in exclusion from the analysis of the response rate. Precise definitions for categories 4-9 will be protocol specific.

All conclusions should be based on all eligible patients. Subanalyses may then be performed on the basis of a subset of patients, excluding those for whom major protocol deviations have been identified (*e.g.*, early death due to other reasons, early discontinuation of treatment, major protocol violations, etc.). However, these subanalyses may not serve as the basis for drawing conclusions concerning treatment efficacy, and the reasons for excluding patients from the analysis should be clearly reported. The 95% confidence intervals should also be provided.

REFERENCES

- 1. Navaneelan, T., *Trends in the incidence and mortality of female reproductive system cancers. Health at a Glance.* Statistics Canada catalogue 201. **no. 82-624-X.**
- 2. Fung-Kee-Fung, M., et al., *Optimal chemotherapy treatment for women with recurrent ovarian cancer*. Curr Oncol, 2007. **14**(5): p. 195-208.
- 3. Tania, M., M.A. Khan, and Y. Song, *Association of lipid metabolism with ovarian cancer*. Curr Oncol, 2010. **17**(5): p. 6-11.
- 4. Pyragius, C.E., et al., *Aberrant lipid metabolism: an emerging diagnostic and therapeutic target in ovarian cancer.* Int J Mol Sci, 2013. **14**(4): p. 7742-56.
- 5. Hedditch, E.L., et al., *ABCA transporter gene expression and poor outcome in epithelial ovarian cancer.* J Natl Cancer Inst, 2014. **106**(7).

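### The Simon test uses inconsistent denominators: stage 1 counts response-evaluable patients, while 13.5.2 bases conclusions on all eligible patients with early death and unknown status as failures

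*Protocol*

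**What the plan says.** Four descriptions of the population stand side by side in the protocol.

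- **Stage 1, Synopsis and 13.2:** "9 response evaluable patients will be entered in the first stage". The pooling rule repeats it: "A total (between phase 1 and phase 2 stage 1) of 9 response evaluable patients treated at RP2D are required".
- **Stage 1, 13.1.2:** the trigger for expansion is read after nine patients have been *treated* at the RP2D. Evaluability is not mentioned.
- **Stage 2, Synopsis and 13.2:** 25 further patients are *accrued*, and the success count is taken from those accrued.
- **Main analysis of response, 13.5.2:** "All conclusions should be based on all eligible patients". Of the response categories it lists, "Patients in response categories 4-9 should be considered to have a treatment failure (disease progression)"; these include early death from any cause and unknown status. Analyses that leave patients out, for example for early discontinuation, may not support efficacy conclusions.

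Section 11.1.1 defines evaluability for objective response: measurable disease at baseline, and patients who "have received at least one cycle of therapy, and have had their disease re-evaluated will be considered evaluable for response". A note adds back patients with objective progression before the end of cycle 1. Section 11.1.7 defines the response rate as a proportion of patients, with no restriction to evaluable ones.

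**The concern.** Both rules are fixed in the protocol, and they cannot both govern the same test. The nine patients who decide whether 25 more are enrolled are chosen under a definition that 13.5.2 does not accept as a basis for conclusions.

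The exclusion depends on outcome. The first response scan comes at 8 weeks (11.1). Patients who stop for clinical progression need no further scan: the follow-up table in 5.6 marks none for them, and note g to the Section 10 calendar asks for scans only from patients who stop for other reasons. The note in 11.1.1 readmits only *objective* progression, and only before the end of cycle 1. This leaves early deaths, clinical deterioration without a scan, and stops within cycle 1 without objective progression. Nearly all of these are non-responders. Replacing them gives extra chances of finding the response that opens stage 2, and if the same counting is carried into stage 2, extra chances of declaring activity.

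**Working it through.** **Inputs from 13.2.** The procedure is said to "test the null hypothesis that the response rate is 15% versus alternating hypotheses that the response rate is 35%". Alpha "is α =0.05 and the power" "is 0.81 when true response rate is 20%". Printed rule: stop if 0 of 9 respond, otherwise accrue 25, active if 8 or more of those 25 respond. Expected sample size is given as 19 under the null and 25 under the alternative.

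**Formula.** With stage 1 response probability p1 and stage 2 probability p2,

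P(active) = Σ over x > r1 of P(Bin(9, p1) = x) × P(Bin(25, p2) ≥ R − x)

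when responses are counted cumulatively against R. Where the success count uses stage 2 alone, this becomes P(Bin(9, p1) > r1) × P(Bin(25, p2) ≥ R).

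**Reproducing the stated figures.**

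- Printed rule, p = 0.15: (1 − 0.85^9) × P(Bin(25, 0.15) ≥ 8) = 0.768 × 0.0255 = 0.0196. Power at 35% is 0.680. Expected N is 28.2 and 33.5. These are not the stated values.
- The printed 8 read cumulatively out of 34: alpha 0.121, power 0.933. Not the stated values either.
- Stop at ≤1/9, active at ≥9/34: alpha 0.0474, power 0.811 at 35%, expected N 19.0 under the null and 31.0 under the alternative. This matches the stated alpha bound, the 0.81 and the 19. The protocol does not print these cut-offs.

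Because it is unclear which rule is meant, both the matching design and the printed rule are carried forward.

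**Effect of the evaluable restriction.** The protocol gives no non-evaluable share, so call it q and *assume* 5–20%. Assume that all non-evaluable patients are non-responders and that the true rate among all eligible treated patients is 15%. The rate among evaluable patients is then 0.15/(1 − q). *Stage 1 only* puts that rate in p1 and keeps p2 = 0.15; *both stages* puts it in p1 and p2.

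| q | Evaluable rate | ≤1/9, ≥9/34: stage 1 only | ≤1/9, ≥9/34: both stages | Printed rule: stage 1 only | Printed rule: both stages |
|---|---|---|---|---|---|
| 0 | 15.0% | 0.0474 | 0.0474 | 0.0196 | 0.0196 |
| 5% | 15.8% | 0.0523 | 0.0622 | 0.0200 | 0.0265 |
| 10% | 16.7% | 0.0579 | 0.0818 | 0.0205 | 0.0361 |
| 15% | 17.6% | 0.0644 | 0.1079 | 0.0210 | 0.0494 |
| 20% | 18.8% | 0.0722 | 0.1424 | 0.0215 | 0.0682 |

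**Effect on the futility gate alone.** Under the printed stop at 0/9, the chance of stopping an ineffective regimen is (1 − p1)^9: 0.85^9 = 0.232 with all patients counted, 0.194 at q = 10%, and 0.8125^9 = 0.154 at q = 20%.

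**The case against.** **The restriction is written for stage 1 only.** Stage 2 says accrued and 13.1.2 says treated. In stage 1 it acts on a futility gate, not on the declaration of activity. This stands. A reader might infer that the whole Simon decision counts evaluable patients only, but the text does not say so. The mixed wording is still part of the defect, because it leaves each stage's denominator open.

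**The alpha effect may be small.** A reader might infer that the restriction roughly doubles alpha. The documents do not support that. For the ≤1/9, ≥9/34 design, doubling needs q of about 12.7%, every excluded patient a non-responder, and exclusion in both stages; with stage 1 alone affected it needs about 31%. Under the printed rule with stage 1 alone affected, alpha barely moves. With both stages affected it doubles at about 11.4% but is still just under 0.05 at q = 15%.

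**Not all early failures are dropped.** Objective progression before the end of cycle 1 is kept. Patients who stop for toxicity after a full cycle are still scanned every 12 weeks and can become evaluable. Section 11.1.4.3 asks for every effort to document progression after symptomatic deterioration. This narrows the group that is lost but does not empty it: effort to document is not a required scan, and a patient who has died cannot be scanned.

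**The reported response rate is already protected by 13.5.2.** That is correct if 13.5.2 is followed. It does not protect the interim decision, which 13.2 ties to evaluable patients.

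**Conclusion.** The contradiction is certain: 13.2 and the Synopsis, read with 11.1.1, conflict with 13.5.2, and 13.1.2 and the stage 2 wording add two further descriptions. The direction is also clear: leaving out unscanned non-responders can only make continuing, and declaring activity, more likely.

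The size is conditional. Over an assumed q of 5–20%, alpha moves from 0.047 to 0.052–0.072 (stage 1 only) or 0.062–0.142 (both stages) for the design that matches the stated alpha and power. For the printed rule it moves from 0.020 to 0.020–0.022 or 0.027–0.068. These figures assume that every non-evaluable patient is a non-responder and that the 15% null refers to all eligible treated patients. The mismatch between the printed cut-offs and the stated alpha and power is a separate matter and is not settled here.

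This should be fixed. It is not graver than that, because response rate is a secondary endpoint and 13.5.2 already sets the right rule for reporting it.

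**What to change.** In the Synopsis, 13.1.2 and 13.2, use one denominator for both stages, consistent with 13.5.2: eligible patients treated at the RP2D who received at least one dose, including phase I patients at that dose. Count everyone without a complete or partial response as a non-responder, that is, categories 3–9 of 13.5.2. Stable disease must be named, because the failure clause in 13.5.2 starts at category 4. Keep the 11.1.1 evaluable set for a sensitivity analysis only. Whether the final count runs over 25 or 34 patients should be settled with the cut-offs, not through this edit.

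The cost is wording. No extra patients are needed, since non-evaluable patients would no longer be replaced. The response rate in the decision may be slightly lower than among evaluable patients.
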